9.7.1.8 Other Analyses

Palatability and Acceptability Questionnaire

Measurement of palatability will be assessed using the Hedonic scale ([Guinard, 2001](#)) which is a Visual Analog Scale (VAS).

Expansion Phase Analyses

Safety data for Cohort 3B (Combination Expansion) will be reported at a later date.

9.7.2 Determination of Sample Size

Approximately 69 to 108 subjects are planned for this study as follows:

Cohort 1 (Single-Agent Dose-Finding): Approximately 12 to 24 subjects based on TiTE-CRM algorithm.

Cohort 2 (Single-Agent Expansion): Approximately 27 to 42 subjects: Cohort 2A: DTC group (12 subjects) and Cohort 2B: osteosarcoma group (15 to 30 subjects).

Cohort 2A: DTC Group

Approximately 12 subjects with evaluable or measurable disease are planned to be enrolled in Cohort 2A due to limited number of pediatric patients with DTC.

Cohort 2B: Osteosarcoma Group

A minimum of 15 PFS-4 evaluable subjects will be assessed in cohort 2B. The sample size estimates were based on Simon's Optimal Two-Stage Design ([Simon, 1989](#)). If fewer than 5 subjects who are alive and free of disease progression at 4 months after first dose date are observed among the first 15 evaluable subjects in Stage I, accrual in the cohort will be suspended. Otherwise, if at any time during Stage I of the cohort, at least 5 subjects who are alive and free of disease progression at 4 months after first dose date are recorded among the first 15 evaluable subjects, enrollment in the cohort will continue seamlessly for a total of approximately 27 evaluable subjects. If, at the end of the second stage for the cohort, at least 10 subjects who are alive and free of disease progression at 4 months are recorded among the 27 subjects in the cohort, study drug will be considered active in the population.

The above sample size estimates are based on the following assumptions: the null hypothesis PFS-4 (H_0) is $\leq 25\%$, and the alternative hypothesis PFS-4 (H_1) is $\geq 45\%$. One-sided Type I error (α) = 0.1, and power = 80%. To account for nonevaluable subjects, a total of 15-30 osteosarcoma subjects will be enrolled for Cohort 2B.

Cohort 3A (Combination Dose-Finding)

Approximately 12 to 24 osteosarcoma subjects for whom ifosfamide and etoposide are considered a treatment option

Cohort 3B (Combination Expansion)

With the following assumptions: $p_0=25\%$, $p_1=50\%$, 1-sided $\alpha=10\%$, $\beta=20\%$, where p_0 is an unacceptable rate of PFS, p_1 is the target rate of PFS, α is the probability of declaring lenvatinib effective when the true rate is p_0 , and β is the probability of declaring lenvatinib not effective if the true rate is p_1 , a sample size of 15 subjects will provide a statistical power of 80%. To account for nonevaluable subjects, a total of 18 lenvatinib-naïve subjects will be enrolled for Cohort 3B, along with some subjects from Cohorts 1 and 2B.

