The null hypothesis that PFS-4 is $\leq 25\%$ will be tested against the alternative hypothesis of a PFS-4 $\geq 45\%$, using the 1-sample exact test of a single proportion, at the 1-sided 0.1 level. PFS-4 will be presented with corresponding 2-sided, exact binomial 80% and 95% CIs. This analysis will be performed on the Safety Analysis Set.

Cohort 3 (Combination Dose-Finding and Expansion)

Cohort 3A: Osteosarcoma Combination Dose-Finding

As in Cohort 1, the DLT will be assessed to determine the RD of lenvatinib in combination with ifosfamide plus etoposide. DLTs occurring during Cycle 1 will be evaluated and the subjects will be assigned a dose based on the rules for dose escalation and de-escalation (see [Section 9.1.2.3 Treatment Phase: Cohort 3A](#)).

This dose of lenvatinib will be used to treat additional osteosarcoma subjects in Cohort 3B.

Cohort 3B (Osteosarcoma Combination Expansion)

The primary efficacy endpoint is PFS-4 based on RECIST 1.1.

The null hypothesis that PFS-4 is $\leq 25\%$ will be tested against the alternative hypothesis of a PFS-4 $\geq 50\%$, using the 1-sample exact test of a single proportion, at the 1-sided 0.1 level. PFS-4 will be presented with corresponding 2-sided, exact binomial 80% and 95% CIs. This analysis will be performed on the lenvatinib-naïve subject in Safety Analysis Set, while subjects enrolled from Cohorts 1 and 2B will be summarized only as appropriate.

SECONDARY EFFICACY ANALYSES

Secondary endpoints PFS and TTP will be analyzed using Kaplan-Meier product-limit estimates. Median PFS and the cumulative probability of PFS at 4, and 12 months will be presented with 2-sided, 95% CIs when an adequate number of at risk subjects at those time points warrant the estimate. The cumulative PFS and TTP probabilities will be plotted over time as appropriate.

Secondary endpoints ORR, DCR, and CBR will be calculated with exact binomial 95% CIs.

The endpoint of OS will be analyzed using Kaplan-Meier product-limit estimates. Median OS and the cumulative probability of OS at 12 months will be presented with 2-sided, 95% CIs when an adequate number of at risk subjects at those time points warrant the estimate.

The above analyses will be based on the lenvatinib-naïve subjects in the Safety Analysis Set, while subjects enrolled from Cohorts 1 and 2B will be summarized only as appropriate.

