4 DETERMINATION OF SAMPLE SIZE

Cohort 1: Approximately 12 to 24 subjects based on the TiTE-CRM algorithm in the single-agent dose-finding cohort.

Cohort 3A: Approximately 12 to 24 subjects with osteosarcoma will be enrolled in combination dose-finding cohort.

Cohort 2A: Approximately 12 subjects with evaluable or measurable disease are planned to be enrolled in the DTC cohort.

Cohort 2B: A minimum of 15 PFS-4 evaluable subjects will be assessed in the osteosarcoma single-agent expansion. The sample size estimates were based on Simon's Optimal Two-Stage Design ([Simon, 1989](#)). If < 5 subjects achieve PFS-4 among the 15 evaluable subjects in Stage I, accrual in the cohort will be suspended. Otherwise, if at any time during Stage I of the cohort, ≥ 5 subjects achieve PFS-4 among the 15 evaluable subjects, enrollment in the cohort will continue for a total of approximately 27 evaluable subjects. If, at the end of the second stage for the cohort, ≥ 10 subjects achieve PFS-4 among the 27 subjects in the cohort, lenvatinib will be considered active in the population. The above sample size estimates are based on the following assumptions: the null hypothesis PFS-4 (H_0) is $\leq 25\%$, and the alternative hypothesis PFS-4 (H_1) is $\geq 45\%$. One-sided Type I error (α) = 0.1, and power = 80%. To account for nonevaluable subjects, a total of 15-30 osteosarcoma subjects will be enrolled in Cohort 2B.

Cohort 3B: With the following assumptions: $p_0 = 25\%$, $p_1 = 50\%$, 1-sided $\alpha = 10\%$, $\beta = 20\%$, where p_0 is an unacceptable rate of PFS, p_1 is the target rate of PFS, α is the probability of declaring lenvatinib effective when the true rate is p_0 , and β is the probability of declaring

lenvatinib not effective if the true rate is p_1 , a sample size of 15 subjects will provide a statistical power of 80%. To account for nonevaluable subjects, a total of 18 lenvatinib-naïve subjects will be enrolled in the combination expansion, along with some subjects from Cohorts 1 and 2B.

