5.4.2.1 Primary Efficacy Analyses

COHORT 2A: DTC

The primary efficacy endpoint is ORR for subjects with measurable disease and BOR for all subjects. Tumor response will be based on RECIST 1.1 and assessed every 8 weeks. The analysis will be descriptively performed on the Full Analysis Set.

COHORT 2B: SINGLE-AGENT EXPANSION

The primary efficacy endpoint is the PFS-4 rate based on RECIST 1.1. This is the proportion of subjects free of progression at 4 months. The PFS-4 rate will be estimated using the binomial proportion and the corresponding 80% and 95% exact binomial distribution CIs ([Clopper and Pearson, 1934](#)) will also be provided. The PFS-4 rate will also be tested using a null hypothesis that the PFS-4 rate is $\leq 25\%$ tested against the alternative hypothesis of a PFS-4 rate $\geq 45\%$, using the 1-sample exact test of a single proportion, at the 1-sided 0.1 level. These analyses will be performed on the lenvatinib-naïve subjects in the Full Analysis Set and the Per Protocol Analysis Set.

The PFS-4 rate will be calculated using PFS-4 evaluable subjects. These are defined as follows.

PFS-4 evaluable subjects:

- includes subjects who were treated with study medication at least 16 weeks;
- includes subjects who died or radiologically progressed within 16 weeks after the first administration of study medication. These subjects are not considered free of progression at 4 months;
- includes subjects who received anticancer treatment within 16 weeks after the first administration of study medication. These subjects are not considered free of progression at 4 months;
- excludes those who discontinue the study due to AE or reasons other than disease progression, death, or receiving anticancer treatment within 16 weeks after the first administration of study medication;
- excludes subjects administered any study medication with no baseline or no postbaseline tumor assessments.

COHORT 3B: OSTEOSARCOMA COMBINATION EXPANSION

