13.2 Summary of Efficacy Analyses

Efficacy Variable	Analysis Set	Statistical Method	Tumor Assessments
PFS-4	Full Analysis Set, Per Protocol Analysis Set	Number (percent) of subjects who are alive, free of disease progression, and did not receive anticancer medication 4 months after the first dose, and its exact 80 and 95% CIs using method of Clopper and Pearson.	Investigator
		Cohort 2B: PFS-4 rate will be tested using a Null hypothesis that PFS-4 is $\leq 25\%$ tested against the alternative hypothesis of a PFS-4 $\geq 45\%$, using the 1-sample exact test of a single proportion, at the 1-sided 0.1 level.	
ORR	Full Analysis Set, Per Protocol Analysis Set	Cohort 3B: PFS-4 rate will be tested using a Null hypothesis that PFS-4 is $\leq 25\%$ tested against the alternative hypothesis of a PFS-4 $\geq 50\%$, using the 1-sample exact test of a single proportion, at the 1-sided 0.1 level.	Investigator
PFS	Full Analysis Set, Per Protocol Analysis Set	Number (percent) of subjects (with PR + CR) and its exact 95% CI using method of Clopper and Pearson.	Investigator
OS	Full Analysis Set	KM method: Median, Q1, and Q2 PFS will be presented, with 2-sided 95% CIs (Brookmeyer and Crowley). Cumulative probability of PFS at 4 and 12 months will be presented with 2-sided 80 and 95% CIs (Greenwood using the log-log). KM plot will also be provided.	Not Applicable

Efficacy Variable	Analysis Set	Statistical Method	Tumor Assessments	
		plot will also be provided.		
BOR	Full Analysis Set, Per Protocol Analysis Set	Number (percent) and 95% exact CIs will be provided for each BOR category	Investigator	
DOR	Full Analysis Set, Per Protocol Analysis Set	KM method: Median, Q1, and Q2 PFS will be presented, with 2-sided 95% CIs (Brookmeyer and Crowley).	Investigator	
TTP	Full Analysis Set, Per Protocol Analysis Set	Kaplan-Meier method: Median, Q1, and Q2 TTP will be presented with 2-sided 95% CIs (Brookmeyer and Crowley). Cumulative probability of TTP at 4 and 12 months will be presented with 2-sided 80 and 95% CIs (Greenwood using log-log). Kaplan-Meier plot will also be provided.	Investigator	

Efficacy Variable	Analysis Set	Statistical Method	Tumor Assessments
DCR	Full Analysis Set	Number (percent) of subjects (measurable disease with CR + PR + stable disease [SD] \geq 7 weeks, evaluable disease with CR + Non-CR/Non-PD \geq 7 weeks) and its exact 95% CI using method of Clopper and Pearson.	Investigator

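### Cohort 2B: the two-stage rule calls 10/27 active, but the pre-specified exact test gives p = 0.113 there, and the plan does not say which decides

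*Protocol*

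**What the plan says.** **Decision rule.** Protocol 9.7.2 says of Cohort 2B: "The sample size estimates were based on Simon's Optimal Two-Stage Design". Accrual is suspended if fewer than 5 of the first 15 evaluable subjects are alive and progression-free at 4 months. Otherwise it goes on to about 27 evaluable subjects, and the drug counts as active if "at least 10 subjects who are alive and free of disease progression at 4 months are recorded among the 27 subjects in the cohort". The null rate is 25%, the alternative 45%, one-sided alpha 0.1 and power 80%. SAP 4 repeats the rule for 10 or more: "subjects achieve PFS-4 among the 27 subjects in the cohort, lenvatinib will be considered active in the population". Enrolment may run to 30 to allow for nonevaluable subjects.

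**Primary test.** Protocol 9.7.1.5 tests the same null and alternative with a one-sample exact test at one-sided 0.1 and adds: "PFS-4 will be presented with corresponding 2-sided, exact binomial 80% and 95% CIs". SAP 5.4.2.1 does the same, "using the 1-sample exact test of a single proportion, at the 1-sided 0.1 level", and SAP 13.2 reports the proportion "and its exact 80 and 95% CIs using method of Clopper and Pearson".

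Neither set of sections refers to the other. SAP 5.3.3 (multiplicity), SAP 6 (interim analyses) and SAP 7 (changes in the planned analyses) do not rank the two criteria or adjust the inference for the Stage I stop.

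**The concern.** The two-stage rule gets its alpha from the whole design: a trial can reach 10/27 only after passing 5/15. The one-sample exact test treats the 27 subjects as a single fixed sample. It therefore counts, as evidence under the null, paths to 10 or more that Stage I would have stopped. Its p-value is larger than the design's own, and at 10/27 the difference crosses 0.1.

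At that result the study report would call the drug active while its own primary test and 80% interval fail to exclude 25%. With the criteria unranked, the choice could be made after seeing the data, in an open-label cohort whose progression is judged by the investigator (SAP 5.4.2). The stated 80% power also describes only one of the two criteria.

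**Working it through.** **Inputs.** p0 = 0.25, p1 = 0.45, one-sided alpha 0.1, power 80%, n1 = 15 with continuation at 5 or more, N = 27, success at 10 or more (Protocol 9.7.2, SAP 4). Test and intervals are from Protocol 9.7.1.5, SAP 5.4.2.1 and SAP 13.2.

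**1. Reproduce the design.** P(active | p) = Σ over x1 = 5 to 15 of b(15, x1, p) × P[Bin(12, p) ≥ 10 − x1], where b is the binomial probability.

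| x1 | term at p = 0.25 | term at p = 0.45 |
|---|---|---|
| 5 | 0.1651 × 0.1576 = 0.0260 | 0.1404 × 0.6956 = 0.0976 |
| 6 | 0.0917 × 0.3512 = 0.0322 | 0.1914 × 0.8655 = 0.1657 |
| 7 | 0.0393 × 0.6093 = 0.0240 | 0.2013 × 0.9579 = 0.1929 |
| 8 | 0.0131 × 0.8416 = 0.0110 | 0.1647 × 0.9917 = 0.1634 |
| 9 | 0.0034 × 0.9683 = 0.0033 | 0.1048 × 0.9992 = 0.1048 |
| ≥10 | 0.0008 | 0.0769 |
| Sum | **0.0973** | **0.8012** |

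Alpha is 9.7% and power 80.1%, as stated. The chance of stopping early under the null is 0.6865, so expected N is 15 + 0.3135 × 12 = 18.76. A search over two-stage designs with N from 15 to 41 returns this one as the optimal design.

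**2. Apply the named test at the same boundary.**
- P[Bin(27, 0.25) ≥ 10] = 0.1133, above 0.1, so the null is not rejected.
- P[Bin(27, 0.25) ≥ 11] = 0.0528, so the test first rejects at 11/27.
- Clopper-Pearson 80% interval at 10/27: 24.4% to 51.2%, which contains 25%.

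**3. Operating characteristics at N = 27.**

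| Criterion | alpha | power at 45% |
|---|---|---|
| Two-stage, ≥10/27 | 9.7% | 80.1% |
| Stage I stop plus ≥11/27 | 4.9% | 71.2% |
| Single-stage test alone, ≥11/27 | 5.3% | 73.7% |

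**4. Probability of the conflicting result** (Stage I passed, total exactly 10): 0.0973 − 0.0489 = 0.048 at 25% and 0.8012 − 0.7124 = 0.089 at 45%. At 35%, between the design values, it is 0.123.

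**5. Inference that respects the two stages** (stage-wise ordering). The p-value at 10/27 is the two-stage tail, 0.0973. The lower 80% limit solves P(active by ≥10 | p) = 0.10 and the upper solves P(active by ≥11 | p) = 0.90, giving 25.1% to 52.1%. The same method gives a 95% interval of 19.9% to 58.9%. Test, 80% interval and rule then agree.

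**6. Other attained sizes.** The target is approximate, so the smallest cut-off with alpha at or below 0.10 was found for each n, with the 5/15 stop kept.

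| n | two-stage cut-off | alpha | power | single-stage cut-off |
|---|---|---|---|---|
| 26 | 10 | 8.1% | 77.2% | 10 |
| 27 | 10 | 9.7% | 80.1% | 11 |
| 28 | 11 | 6.1% | 75.2% | 11 |
| 29 | 11 | 7.4% | 78.4% | 11 |
| 30 | 11 | 8.8% | 80.9% | 12 |

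Within this range the criteria differ at n = 27 and n = 30. At n = 30 the single-stage tail for 11 or more is 0.1057.

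**The case against.** The strongest reply is that only the two-stage rule has a conclusion attached: the sample-size sections say when the drug counts as active, while the analysis sections say only that the rate is tested and attach no consequence to the result. On that reading the Simon rule decides and the test is reported beside it. The conflict is also a single outcome: at n = 27 both criteria fail at 9 or fewer and both succeed at 11 or more. Ignoring a futility-only stop makes the p-value conservative, and a reader of the report would see the count, the p-value and the interval together.

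The points about scope stand: the disagreement is confined to the boundary, and at n = 27 there is no excess of false positives. The reading itself is reasonable, but neither document states it, and it leaves the pre-specified primary test contradicting the declared conclusion at the design's own cut-off.

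A second reply is that p = 0.113 need not apply to the Protocol test. Protocol 9.7.1.5 uses the Safety Analysis Set, whereas the two-stage rule and the SAP rate use PFS-4 evaluable subjects, so the Protocol denominator could exceed 27. That is correct. The figure holds for the SAP test, and for the Protocol test only if every treated subject is evaluable. It means the two criteria may not even share a denominator, which is a further reason to name one governing analysis.

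**Conclusion.** The concern holds and should be fixed. The two-stage design is sound and meets its stated alpha and power. The fault is that the analysis sections prescribe a single-stage test and intervals that disagree with it at 10/27 (p = 0.113 against a design p-value of 0.097), with nothing to say which prevails. The conflicting result has probability 4.8% at a true rate of 25% and 8.9% at 45%. Depending on the reading, power at 45% is 80.1% or 71.2%.

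These figures assume exactly 27 evaluable subjects, the Stage I rule applied as written, and the same evaluable denominator for both criteria.

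**What to change.** In SAP 5.4.2.1 and 13.2 and Protocol 9.7.1.5, state that the two-stage rule is the primary decision for Cohort 2B. Compute its p-value and its 80% and 95% intervals on the two-stage sample space with stage-wise ordering. Name the same evaluable denominator for the rule, the test and the intervals.

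Because the target is approximate, also give the cut-off for other attained sizes: at least 10 at n = 26, and at least 11 at n = 28, 29 and 30. Among 26 to 30 only 27 and 30 keep 80% power, so restate power if 26, 28 or 29 is reached. The plan does not say that a cut-off of 10 would be carried forward to 28, 29 or 30. If it were, alpha would be 11.4%, 13.1% and 14.7%.

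A less attractive alternative is to keep the exact test, move the rule to at least 11/27 and restate power as 71%.

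The cost is wording and a few lines of code, with no added patients. The SAP revision would be described in the study report (Protocol 9.7.5). The Protocol wording needs an amendment under Protocol 11.1, with regulatory and ethics review if it is judged to affect scientific quality.

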The primary efficacy endpoint is the PFS-4 rate based on RECIST 1.1. This is the proportion of subjects free of progression free at 4 months. The PFS-4 rate will be estimated using the binomial proportion along with the corresponding exact binomial 80% and 95% CIs. The PFS-4 rate will be tested using a null hypothesis that PFS-4 rate is $\leq 25\%$ tested against the alternative hypothesis of a PFS-4 rate $\geq 50\%$, using the 1-sample exact test of a single proportion, at the 1-sided 0.1 level. This analysis will be performed on the lenvatinib-naïve subjects in Full Analysis Set and Per Protocol Analysis Set, while subjects enrolled from Cohorts 1 and 2B will be summarized only as appropriate.

The PFS-4 rate will be analyzed using PFS-4 evaluable subjects. These are defined as follows.

PFS-4 evaluable subjects:

- includes subjects who were treated with study medication at least 18 weeks
- includes subjects who died or radiologically progressed within 18 weeks after the first administration of study medication. These subjects are not considered free of progression at 4 months.
- includes subjects who received anticancer treatment within 18 weeks after the first administration of study medication. These subjects are not considered free of progression at 4 months.
- excludes those who discontinue the study due to AE or other reasons than disease progression, death , or receiving anticancer treatment within 18 weeks after the first administration of study medication
- excludes subjects administered any study medication but had no baseline or no postbaseline tumor assessments.

SURGICALLY REMOVED LESIONS

For Cohorts 2B, 3A and 3B, removal of existing (not new) osteosarcoma metastatic lesion(s) is permitted after the completion of the first 4 months of the treatment period without PD. The time points for tumor response assessment after tumor removal will be considered ‘Not Evaluable’ unless the tumor response is considered PD for the following reasons:

- appearance of an unequivocal new lesion
- unequivocal progression of non-target lesions or target lesions

Lesions removed before the first 4 months are permitted only in the case of PD.

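### Cohort 3B: the stated 80% power with 15 subjects is 69.6% under the planned exact test, and no number up to the planned 18 reaches 80%

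*Protocol*

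**What the plan says.** Protocol 9.7.2 sets the Cohort 3B assumptions: an unacceptable PFS-4 rate of 25%, a target rate of 50%, one-sided alpha 10% and beta 20%. It defines alpha and beta as the probabilities of a wrong declaration in each direction. It then states that "a sample size of 15 subjects will provide a statistical power of 80" per cent. The protocol synopsis and SAP section 4 repeat this. To allow for nonevaluable subjects, "a total of 18 lenvatinib-naïve subjects will be enrolled for Cohort 3B".

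The analysis is specified separately. SAP 5.4.2.1 tests the hypothesis "using the 1-sample exact test of a single proportion, at the 1-sided 0.1 level". The synopsis, Protocol 9.7.1.5 and SAP Appendix 13.2 name the same test. On the denominator, SAP 5.4.2.1 says: "The PFS-4 rate will be analyzed using PFS-4 evaluable subjects".

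The documents do not name the method behind the figure of 15. For Cohort 2B they give success counts (5 of 15, then 10 of 27). For Cohort 3B they give none.

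**The concern.** With a small sample the exact binomial test can use only a few type I error levels, and it is usually well below its nominal alpha. Power for such a test has to be computed from the binomial distribution at the actual cut-off. The pair of 15 subjects and 80% looks like the output of a large-sample formula.

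This is the primary hypothesis test of the combination expansion cohort. If the real power is lower, a non-significant result would be read against a 20% chance of missing an active combination when the chance is larger. There is also a practical risk. A reader who relies on the 80% claim would look for a cut-off that delivers it. At 15 subjects that cut-off is 6, whereas the exact test requires 7.

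**Working it through.** **Inputs.** p0 = 0.25, p1 = 0.50, one-sided alpha = 0.10, beta = 0.20, n = 15 evaluable, 18 enrolled (Protocol 9.7.2; SAP section 4). Test: one-sample exact binomial (Protocol 9.7.1.5; SAP 5.4.2.1).

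**Step 1. Reproduce the plan's figure.** The one-sample normal approximation without continuity correction gives

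n = [(z₀.₉₀ √(p0(1−p0)) + z₀.₈₀ √(p1(1−p1))) / (p1−p0)]²
= [(1.2816 × 0.4330 + 0.8416 × 0.5) / 0.25]² = 15.23.

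At n = 15 the same formula gives power Φ[(0.25√15 − 1.2816 × 0.4330) / 0.5] = 79.6%. So 15 subjects and 80% power can be reproduced, but by a method that the documents do not name and do not use for the analysis.

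**Step 2. Apply the named test at n = 15.** The cut-off r is the smallest count with P(X ≥ r | 15, 0.25) ≤ 0.10.

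- r = 6: P(X ≥ 6 | 0.25) = 0.1484, which exceeds 0.10. Power would be P(X ≥ 6 | 0.50) = 27824/32768 = 0.8491.
- r = 7: P(X ≥ 7 | 0.25) = 0.0566, which is allowed. Power is P(X ≥ 7 | 0.50) = 22819/32768 = 0.6964.

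No cut-off at 15 meets both alpha ≤ 10% and power ≥ 80%. The uncorrected z test at n = 15 rejects at 6 or more, so its true type I error is 14.8%.

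**Step 3. Repeat for other numbers of evaluable subjects.**

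| n | Success if at least | Attained alpha | Power at 50% | False-negative risk |
|---|---|---|---|---|
| 13 | 6 | 0.0802 | 0.7095 | 0.2905 |
| 14 | 7 | 0.0383 | 0.6047 | 0.3953 |
| 15 | 7 | 0.0566 | 0.6964 | 0.3036 |
| 16 | 7 | 0.0796 | 0.7728 | 0.2272 |
| 17 | 8 | 0.0402 | 0.6855 | 0.3145 |
| 18 | 8 | 0.0569 | 0.7597 | 0.2403 |
| 19 | 8 | 0.0775 | 0.8204 | 0.1796 |
| 20 | 9 | 0.0409 | 0.7483 | 0.2517 |
| 21 | 9 | 0.0561 | 0.8083 | 0.1917 |

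Over all n from 10 to 18 the highest power is 77.3%, at n = 16. The first n to reach 80% is 19. Power falls below 80% again at 20, and it stays above 80% from 21 up to 30, the largest n checked. The rise and fall comes from the discreteness of the binomial.

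**Step 4. Size of the gap.** At n = 15 power is 80 − 69.6 = 10.4 points below the stated value, and the false-negative risk is 30.4/20 = 1.52 times the stated one. At n = 16, 17 and 18 the shortfall is 2.7, 11.5 and 4.0 points.

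**The case against.** The strongest reply is that this is not an arithmetic slip. The figure follows from a standard approximation, and the decision itself remains sound. The exact test keeps type I error at or below 10% at every n (4.0% to 8.0% for n = 15 to 18). It fixes the cut-off once n is known, and the estimate will be reported with exact 80% and 95% confidence intervals. All of that is true, and it means that only the power statement is wrong. It does not make the power statement true for the test that will be run. That the approximation was the source is also an inference.

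A second reply is that the false-negative risk of 30% belongs to n = 15. Protocol 9.7.1.5 runs the test on lenvatinib-naïve subjects in the Safety Analysis Set, which could be about 18. Power there is 76.0%, a gap of 4 points. This narrows the shortfall in that case, but 15 is the plan's own number, and the SAP restricts the analysis to PFS-4 evaluable subjects. At 17 the shortfall is larger than at 15.

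Third, several places in the protocol say approximately 18, so 19 evaluable subjects is not impossible. That stands, but the plan does not aim for 19. The SAP's exclusions for early discontinuation and missing tumour assessments could equally take the number below 15.

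**Conclusion.** The concern holds. Under the named exact test, 15 subjects give 69.6% power at an attained one-sided alpha of 5.7%, against the stated 80% and 10%. No number up to the planned 18 reaches 80%. At 15 evaluable subjects the chance of missing a combination with a true PFS-4 rate of 50% is 30.4%; over 15 to 18 it ranges from 22.7% to 31.5%.

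These figures rest on the plan's own rates, on one final test without an interim look, and on independent binary outcomes in the evaluable subjects. Control of type I error is not affected. The power claim is wrong as written for the primary test of this cohort, and it should be corrected before the result is interpreted.

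**What to change.** In Protocol 9.7.2, the protocol synopsis and SAP section 4, replace the 80% power statement for Cohort 3B with the exact operating characteristics:

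- 15 evaluable: success at 7 or more, attained alpha 5.7%, power 69.6%
- 16 evaluable: 7 or more, 8.0%, 77.3%
- 17 evaluable: 8 or more, 4.0%, 68.5%
- 18 evaluable: 8 or more, 5.7%, 76.0%

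It would help to add the rows for 13, 14 and 19 from the table above, since the evaluable number may fall outside 15 to 18. The cut-off moves from 7 to 8 between 16 and 17, so the table should be fixed before the evaluable number is known.

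This costs wording only: no extra patients, no new procedures and no change of test. The price is a less favourable power figure. If the sponsor wants to keep the 80% claim with the exact test, the evaluable target would have to be exactly 19, or at least 21, which does mean more patients.
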